8.5 Withdrawal of Consent

Participants or their Personal Consultee/Welfare Guardian/Registered Medical Practitioner may withdraw the patient from the study at any time without prejudice. In the event of a request to withdraw, only anonymised data recorded up to the point of withdrawal will be included in the study analysis and any stored samples from such participants will be destroyed.

9. SCHEDULE OF ASSESSMENTS AND STUDY PROCEDURES

9.1 Schedule of Assessments

All patients will be evaluated during the study and data collected at each of the following time-points. For routinely collected clinical data the NHS record will be the source document and for study specific clinical measurements the CRF will be the source document.

Baseline

- Patient Demographics (date of birth, gender)
- Date and Time of ICU admission
- Suspected Source of Sepsis
- The Acute Physiology and Chronic Health Evaluation score (APACHE II) at ICU admission

At Sampling

- Site, Date and Time of sampling
- Previous Antibiotic regimens within 3 calendar days of sampling (Yes/No)
- Determinants of SOFA Score at time of sampling

Additional Assessments

- Paired blood culture result
- Multiplex PCR result
- Date and Time Multiplex PCR test completed
- Date and Time clinical team informed of blood culture result
- Results of additional blood and other sterile anatomic site cultures taken within +/-7 days of the research blood sample for suspected sepsis will also be recorded.
- Results of cultures from non-sterile anatomic sites within +/-3 days of the research blood sample for suspected sepsis will be recorded. Whether the treating physician judged this to represent a clinically-suspected focus of infection will also be recorded.

At Discharge

- Date of critical care discharge
- Date of hospital discharge

Mortality

- Date of death (within 28 days of recruitment)

9.2 Study Procedures

9.2.1 Blood Sampling

Blood cultures will be taken in the usual manner, for the participating study site, in the course of routine care. At the time that each blood culture is taken from an eligible patient, a 5ml sample of blood will also be collected for multiplex PCR testing. An additional 10ml sample of blood will also be collected where

- (i) it is the first sample
- (ii) research staff are available to process and store the sample

In patients meeting these criteria, and where resources permit, a further 3ml sample of blood will be taken into RNA preservation reagent (Tempus) tubes.

The research blood will be obtained from the same sampling event as the matched blood culture (i.e. from the same syringe draw); if this is not possible then research blood should be obtained by the same sampling technique (i.e. venepuncture or accessing the same vascular device).

When multiple sampling sites are being used for routine clinical blood cultures at the same time, the peripheral (venepuncture) sample is preferred for matched sampling in this study. If a peripheral sample is not being obtained in routine clinical care, then obtaining matched research and routine culture samples from a vascular access device is acceptable.

At participating sites in England, Wales and Northern Ireland, patients undergoing blood culture in the course of routine clinical care will have a research blood sample taken at the same time. The research blood sample will be stored pending informed consent/assent being obtained within 72 hours of taking the sample. No research blood samples will be tested until consent/assent for participation in this study has been obtained. In the event that consent/assent is not obtained the entire research sample will be discarded with no research tests being carried out on it.

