The concept of a 'golden hour' of assessment and intervention, initially described in other clinical settings, is therefore now well established in sepsis management¹². In SSC guidelines, both blood culturing and the administration of broad-spectrum empirical antibiotic treatment are recommended in the first hour after the recognition of potential sepsis. A 2010 review of the implementation of SSC guidelines across two continents demonstrated a 5.4% improvement in mortality even with only limited compliance¹⁶ although several studies also show that the empirical antibiotics received by 20-40% of patients in ICU are found to be inappropriate when the pathogen is later identified^{13,17}. Therefore, a rapid test for pathogen identification offers the opportunity to improve patients' treatment and outcomes.

Microbiological sampling in sepsis is independently associated with patients' survival¹⁸ and the SSC recommends at least two samples for traditional culture prior to the administration of antibiotics, within the first hour¹¹. Evidence on the sensitivity of blood cultures is conflicting¹⁹. The value certainly varies with the pathogen, but it is well accepted that it only approaches 100% by increasing the number of samples taken²⁰.

The emergence of multi drug resistant pathogens has gone from concerning case report to a challenging global priority over recent years- with particular relevance and incidence in intensive care settings worldwide^{21,22}. Empirical antibiotics contribute to resistance²³⁻²⁵ but remain essential to management with existing microbiological techniques that cannot provide a point of care result to identify a pathogen and guide more appropriate prescription²⁶. There is agreement that current diagnostic tools for sepsis are inadequate²⁷. The clinical need is clear: new, rapid, diagnostic methods that will facilitate prompt treatment with, effective, antibiotic therapy. To have an impact on patient management and outcomes, a novel diagnostic test in sepsis is required to be truly point of care, to provide ease of use, economy and portability, with a time to result of less than one hour.

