5. OUTCOME MEASURES

5.1 Primary Outcome Measure

The primary outcome measure is diagnostic accuracy of the multiplex PCR test, expressed as sensitivity, specificity, and positive and negative predictive values, with uncertainty expressed using 95% confidence limits.

In the primary analysis, these will be calculated by using the paired blood culture as the reference standard (i.e. the blood culture that had been taken contemporaneously). True positivity will be defined as the PCR test detecting the same genus of organism as identified in the paired blood culture.

Acknowledging that there is no perfect reference standard for sepsis, a secondary analysis will be undertaken, using a less stringent reference standard to resolve discrepant results in a 'fair umpire' test³⁷. This will be applied when the PCR test is positive and the paired blood culture is negative. In this analysis, true positivity will be defined as either:

- (i) culture of the same genus of organism in blood or other sterile site culture within 7 days of the test sample being taken; or
- (ii) culture of the same genus of organism from a non-sterile anatomic site within 3 days of the test sample being taken which is judged, by the patient's clinical team, to represent a focus of infection.

Furthermore we will undertake analysis of the primary outcome measure when multiplex PCR testing is conducted at the point of care, vs. centrally, using both the paired blood culture and the fair umpire test. The primary outcome (diagnostic accuracy) will be re-analysed including only those samples tested at the point of care and compared to the same metrics obtained when only those samples tested centrally are included.

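### A simultaneous second culture set stays outside the primary reference, and the one-sided fair-umpire analysis cannot reveal the PCR misses it would show

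*Protocol*

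**What the plan says.** Protocol 5.1 measures accuracy against the paired blood culture, glossed as "i.e. the blood culture that had been taken contemporaneously". It adds: "True positivity will be defined as the PCR test detecting the same genus of organism as identified in the paired blood culture".

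Protocol 9.2.1 sets out how the pair is formed. Research blood comes from the same syringe draw as the matched culture or, failing that, is taken by the same technique. For the situation "When multiple sampling sites are being used for routine clinical blood cultures at the same time", the rule is that "the peripheral (venepuncture) sample is preferred for matched sampling in this study".

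Protocol 9.1 records the paired result as one item. Other blood cultures within 7 days either side are a separate item.

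The background (3.2.1) states that "the SSC recommends at least two samples for traditional culture prior to the administration of antibiotics". On the sensitivity of blood culture it says that "it only approaches 100% by increasing the number of samples taken".

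Section 5.1 also plans a secondary fair-umpire analysis. It is triggered only by a positive PCR with a negative paired culture. It counts the PCR result as true if, among other routes, the same genus grows in blood within 7 days.

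**The concern.** The protocol expects several sets at one time and says that a single set is incomplete, yet one set alone decides the primary reference. Section 7.4 requires at least 5 days between a patient's samples, so the other set cannot form a PCR pair of its own.

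When the matched set is negative and the simultaneous set grows a pathogen, two misclassifications are possible:

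- **PCR positive:** counted as a false positive, which lowers specificity and positive predictive value.
- **PCR negative:** counted as a true negative, which hides a miss and flatters sensitivity and negative predictive value relative to all culture taken at that event.

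The planned secondary analysis acts on the first and not on the second. A reader who sees sensitivity hold or improve under the umpire could take that as reassurance, although the rule allows no other direction for these samples.

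**Working it through.** **1. Classification.** Take a sample with a negative matched set and the organism in the simultaneous second set only.

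| PCR | Primary (matched set) | Fair umpire | Any-set reference |
|---|---|---|---|
| Positive, same genus | False positive | True positive | True positive |
| Negative | True negative | True negative (not examined) | False negative |

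**2. The plan's own figures (protocol 11.1).** Positives needed = 1.96² × Se(1 − Se)/d², rounded up and divided by the event rate.

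- Overall: 3.8416 × 0.09/0.0009 = 384.2, so 385; 385/0.10 = 3850 (stated 3851).
- Uncommon pathogens: 3.8416 × 0.09/0.04 = 8.6, so 9; 9/0.002 = 4500 (stated 4501).

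Both reproduce to within one sample, and this point does not affect them.

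**3. Inputs for the size.** From 11.1: 4501 samples, 10% positive, sensitivity 90%, specificity 95%. This gives 450 matched positives (405 detected) and 4051 matched negatives.

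Three inputs are assumptions, because the documents give none of them:

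- m, the share of draws that are multi-set: 25-100%
- y, second-set-only positives as a fraction of matched positives: 5-30%
- s, PCR detection in those samples: 50-90%

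**4. Formulas.**

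- Affected samples: x = 450 × m × y
- Primary false positives among them: s·x; hidden misses: (1 − s)·x
- Primary specificity = 1 − [0.05(4051 − x) + s·x]/4051
- Primary sensitivity = 405/450 = 90% throughout
- Umpire sensitivity = (405 + s·x)/(450 + s·x)
- Any-set sensitivity = (405 + s·x)/(450 + x)

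**5. Results.**

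| m | y | s | x | False positives | Hidden misses | Primary specificity | Umpire sensitivity | Any-set sensitivity |
|---|---|---|---|---|---|---|---|---|
| 25% | 5% | 90% | 5.6 | 5.1 | 0.6 | 94.9% | 90.1% | 90.0% |
| 25% | 5% | 50% | 5.6 | 2.8 | 2.8 | 94.9% | 90.1% | 89.5% |
| 100% | 10% | 70% | 45 | 31.5 | 13.5 | 94.3% | 90.7% | 88.2% |
| 100% | 30% | 90% | 135 | 121.5 | 13.5 | 92.2% | 92.1% | 90.0% |
| 100% | 30% | 50% | 135 | 67.5 | 67.5 | 93.5% | 91.3% | 80.8% |

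The worst specificity and the worst sensitivity come from different rows: the first needs high PCR detection, the second low. In the middle row, primary positive predictive value is 405/(405 + 231.8) = 63.6%. Against any set it is 436.5/(436.5 + 200.3) = 68.5%.

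**6. Comparison with precision.** The half-width for specificity is 1.96 × √(0.95 × 0.05/4051) = 0.67 points. The target for sensitivity is ±3 points.

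- The specificity shift is x(s − 0.05)/4051. It passes 0.67 points when x exceeds about 32 at s = 90% (7% of 450), or about 60 at s = 50% (13%).
- The sensitivity shift is (0.9 − s)x/(450 + x). It passes 3 points when x exceeds about 36 at s = 50% (8%), or about 79 at s = 70% (18%). At s = 90% it is zero.

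**The case against.** Same-draw matching is a deliberate and defensible choice. It compares PCR on a blood draw with culture of that draw. An any-set reference sets one 5 ml PCR sample against two or more culture draws, so an apparent miss may be a matter of sampling and not assay failure. Cultures follow each site's usual practice, so the number of sets, and with it the strength of an any-set reference, would vary. Growth from a second set drawn through a line may be contamination or colonisation. These arguments stand, and they are good reasons to keep the matched set as primary.

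A reader might infer more than the documents support:

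- **That 5.1 and 9.2.1 contradict each other.** They do not. Section 5.1 speaks of one paired culture, 9.2.1 says how the pair is formed, and 9.1 records it apart from other cultures. The gloss about timing in 5.1 is merely loose where two sets are contemporaneous.
- **That the false positives go uncorrected.** A simultaneous second set with the same genus satisfies the umpire's 7-day blood culture route, so these cases are reclassified in the secondary analysis.
- **That the bias necessarily exceeds the planned precision.** With x = 45 and s = 60%, specificity falls by 45 × 0.55/4051 = 0.6 points and any-set sensitivity by 0.3 × 45/495 = 2.7 points. Both lie within the half-widths, and with few multi-set draws the effect is negligible.

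It can also be said that the hidden misses come from the umpire's one-sided trigger, and that 11.5 leaves additional analyses to the SAP. The first is true, but it is the single-set reference that leaves those samples for the umpire to resolve. As to the second, 5.1 itself fixes both the secondary reference and its trigger, so the gap lies in the protocol.

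**Conclusion.** The point holds in a limited form. A pathogen grown only in a simultaneous second set produces either a primary false positive, which the umpire can repair, or a hidden PCR miss, which neither 5.1 reference analysis can show. For such samples the umpire can move apparent sensitivity only upward: to between 90.1% and 92.1% over the assumed ranges, while sensitivity against any simultaneous set runs from 90.0% down to 80.8%. Primary specificity runs from about 94.9% down to 92.2%.

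These figures rest on assumed values for the share of multi-set draws, the second-set yield and PCR detection. They also treat every second-set-only isolate as a true pathogen, so they mark out a range and are not an estimate. A larger sample would not remove the bias. The documents do not support replacing the primary reference; they do support adding a symmetric secondary one.

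**What to change.** - Keep the same-draw matched set as the primary reference. State in 5.1 that paired means the set matched under 9.2.1, and that other sets drawn at the same event are not part of the primary reference.
- Pre-specify a secondary analysis whose reference is positive if any blood culture set drawn at the same sampling event grows the organism. Apply it to every sample whatever its PCR result, and report it beside the fair umpire.
- In the CRF, flag which set was matched, which additional sets belong to the same sampling event, and the sampling route of each.

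The cost is small: some wording, one derived variable, a few CRF fields and slightly more analysis. Section 9.1 already collects results of additional blood cultures within 7 days. It does not list their collection times, which is why the same-event flag is needed. The downside is that some line-drawn second-set growth may be contamination or colonisation. Showing the any-set and matched-set results side by side, with the route recorded, would make that visible.

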9.2.2 Sample Processing

The research blood sample will be divided between testing and storage for evaluation of discrepant results and future analyses. The procedure for this will be detailed in the Sample Processing Guideline.

9.2.2.1 Sample for Multiplex PCR Testing

Approximately the first half of the study samples will be initially stored at site and transferred in batches to a central laboratory in Queen's University Belfast, for testing using the Multiplex PCR device, in accordance with the Sample Processing Guideline. Subsequent samples will be analysed using the Multiplex PCR device at the POC by ICU clinical and/or research and/or technical staff at participating sites who have received training in the use of the Multiplex PCR testing device and transferred in batches to a central laboratory in Queen's University Belfast for testing using the Multiplex PCR device.

9.2.2.2 Sample for Storage

The portion of the research blood sample for storage will be transferred to Queen's University Belfast for storage at -80°C and subsequent testing in accordance with the Sample Processing Guideline.

9.2.3 Time to Result

The time required to complete testing will be measured for both Multiplex PCR and the paired blood culture. In the case of the blood culture two measures will be recorded:

- (i) the time between sampling and the test first being reported to clinical teams as positive;
- (ii) the time between sampling and a final pathogen identification first being reported to clinical teams. It is acknowledged that, for both of these, the result will usually be 'first' reported verbally.

Blood cultures that do not flag positive after 5-days of incubation will be categorised as negative with a time to result of 5-days.

9.2.4 Clinical Management of Patients in the Study

There will be no other change to standard care in ICU.

10. DATA COLLECTION & MANAGEMENT

10.1 Data Quality

Data integrity and study credibility depend on factors such as ensuring adherence to the protocol and using quality control measures to establish and maintain high standards for data quality.

The Co-Chief Investigators (CI) and CTU will provide training to site staff on trial processes and procedures including the case report form (CRF) and data collection.

On-site monitoring visits during the trial will check the accuracy of entries on CRF's against the source documents, the adherence to the protocol, procedures and Good Clinical Practice (GCP).

Quality control is implemented by the CTU in the form of Standard Operating Procedures (SOPs), which are defined to encompass aspects of the clinical data management process, and to ensure standardisation and adherence to International Conference of Harmonisation Good Clinical Practice (ICH-GCP) guidelines and regulatory requirements.

Data validation will be implemented and discrepancy reports will be generated following data entry to identify discrepancies such as out of range, inconsistencies or protocol deviations based on data validation checks programmed in the clinical trial database.

10.2 Data Collection

To ensure accurate, complete and reliable data are collected, the CTU will provide training to site staff in the format of investigator meetings and/or site initiation visits.

All data for an individual patient will be collected by the PI or designee and recorded in source documents/electronic CRF for the study. Patient identification on the CRF will be through their unique trial identifier, allocated at the time of recruitment.

Data should be entered onto the online electronic study database as per the CRF entry timelines.

10.3 Data Management

Following the entry of patient data into the study database, the data will be processed as per the CTU Standard Operating Procedures (SOPs). Data queries will be generated for site staff as required to clarify data or request missing information. The designated site staff will be required to respond to these queries within 2 weeks. All queries will be responded to/resolved within the study database. Any amended information will then be entered in the study database.

11. STATISTICAL CONSIDERATIONS

11.1 Sample Size

The sample size is based on:

- (i) an assumed 10% event rate for true positive results among specimens collected – this is based on pilot data collected in a single centre.
- (ii) an estimated overall test sensitivity of 90%, and specificity of 95%.
- (iii) the need to ensure that the overall test sensitivity is estimated with a high degree of precision. We have set this precision as +/-3%, at the 95% confidence level.
- (iv) the ability to assess performance of the test for detecting pathogens for which true positive results are expected as infrequently as 1 in 500 tests. We have set the precision for this as +/-20%, at the 95% confidence level
- (v) Given a 10% event rate for true positive results, a sample size that achieves the proposed degrees of precision for the sensitivity estimate will enable the specificity of the test to be measured with even greater precision.

With an assumed sensitivity of 90% with a 10% true positivity rate, in order to estimate the overall sensitivity of the test with a precision of +/-3% at the 95% confidence level, 3851 samples are required. For uncommon pathogens, with an assumed sensitivity of 90% with a 0.2% true positivity rate, in order to estimate the overall sensitivity of the test with a precision of +/-20% at the 95% confidence level, 4501 samples are required. Therefore, 4501 samples will be tested to assess the diagnostic accuracy of the test using these parameters.

The sample has not been inflated for dropouts or missing data because: (i) research sampling is not necessary after the day of enrolment; (ii) the follow-up period is very short; and (iii) the nature of ICU care presents minimal risk of attrition for follow-up.

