7.4 Recruitment

In order to estimate the overall sensitivity of the test 4501 samples are required and will be tested to assess the diagnostic accuracy of the Multiplex PCR test. This will be achievable given the high incidence of suspected sepsis in the critically ill and the large number of patients expected to meet the eligibility criteria. Each patient can contribute more than one sample to this study; however an interval of at least 5-days must lapse between consecutive samples obtained.

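### Section 11.1 sets N = 4501 from a symmetric ±20-point precision on about 9 positives, but valid 95% limits are strongly asymmetric and reach 32 to 37 points below the estimate

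*Protocol*

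**What the plan says.** Protocol Section 11.1 sets two precision targets for sensitivity.

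- **Overall.** "With an assumed sensitivity of 90% with a 10% true positivity rate", the protocol asks for an estimate "with a precision of +/-3% at the 95% confidence level, 3851 samples are required".
- **Uncommon pathogens.** The study should also be able to assess "pathogens for which true positive results are expected as infrequently as 1 in 500 tests". The target is explicit: "We have set the precision for this as +/-20%, at the 95% confidence level". The calculation reads "For uncommon pathogens, with an assumed sensitivity of 90% with a 0.2% true positivity rate", and then "in order to estimate the overall sensitivity of the test with a precision of +/-20% at the 95% confidence level, 4501 samples are required".

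The larger number is adopted: "Therefore, 4501 samples will be tested to assess the diagnostic accuracy of the test using these parameters". The section names neither the formula nor the interval, does not say how many positives are expected for a 1-in-500 pathogen, and adds no inflation.

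Section 7.4 gives a different reason for the same number: "In order to estimate the overall sensitivity of the test 4501 samples are required".

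**The concern.** The rare-pathogen target alone moves the sample size from 3851 to 4501. At 0.2% frequency, 4501 samples yield about 9 positives. With 90% sensitivity only about 0.9 misses are expected among them, and a symmetric normal interval is not usable there. A reader of ±20% around 90% would expect a lower limit near 70%. If the real lower limit is well below that, the protocol overstates what the study can say about an uncommon pathogen, and it does so on the side where a pathogen is missed.

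There is also a wording conflict. Section 7.4 ties 4501 to overall sensitivity, and the rare-pathogen sentence of 11.1 uses the same phrase, although 11.1 gives 3851 for overall sensitivity.

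**Working it through.** **Inputs (all Section 11.1).** Sensitivity p = 0.90; positivity 10% overall and 0.2% for an uncommon pathogen; half-width d = 0.03 and 0.20; 95% confidence, z = 1.96.

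**1. Reproduce the plan.** Positives needed = z²p(1−p)/d², rounded up, then divided by the positivity rate.

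- Overall: 3.8415 × 0.09 / 0.0009 = 384.1, rounded up to 385; 385 / 0.10 = 3850 (stated 3851).
- Uncommon: 3.8415 × 0.09 / 0.04 = 8.64, rounded up to 9; 9 / 0.002 = 4500 (stated 4501).

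Both agree to within one sample. Sizing on a half-width with Wilson limits would need 10 positives, and with exact limits 13, so neither leads to 4501.

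**2. Write out the planning interval.** 1.96 × √(0.09/9) = 0.196, so 90% ± 19.6 points = 70.4% to 109.6%.

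**3. Actual coverage of that interval with 9 positives and true sensitivity 90%.** At 9/9 it has zero width at 100% and misses 90%. At 8/9, 7/9 and 6/9 it contains 90%. At 5/9 or fewer its upper limit is at most 88.0%, so it misses. Coverage = 0.387 + 0.172 + 0.045 = 0.604.

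**4. Valid intervals with 9 positives.** Wilson: centre (p + z²/2n)/(1 + z²/n), half-width z/(1 + z²/n) × √(p(1−p)/n + z²/4n²). At p = 0.9, n = 9: centre 1.1134/1.4268 = 0.780; half-width (1.96/1.4268) × √(0.0100 + 0.01186) = 0.203. Exact: Clopper-Pearson from beta quantiles, using x = 8.1 for the planning row.

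| Detected | Wilson 95% limits | Half-width / distance below | Exact 95% limits | Half-width / distance below |
|---|---|---|---|---|
| 90% of 9 (planning) | 57.7% to 98.3% | 20.3 / 32 | 53.0% to 99.8% | 23.4 / 37 |
| 9 of 9 | 70.1% to 100% | 15.0 / 30 | 66.4% to 100% | 16.8 / 34 |
| 8 of 9 | 56.5% to 98.0% | 20.8 / 32 | 51.8% to 99.7% | 24.0 / 37 |
| 7 of 9 | 45.3% to 93.7% | 24.2 / 33 | 40.0% to 97.2% | 28.6 / 38 |

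**5. Random number of positives.** Binomial(4501, 0.002) has mean 9.0, a 95% range of 4 to 15, and P(8 or fewer) = 0.455. Averaged over this count and over the number detected:

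- half-width: 20.1 points (Wilson), 23.5 (exact);
- distance to the lower limit: 33 points (Wilson), 38 (exact);
- chance of a half-width of 20 points or less: about 53% (Wilson), 31% (exact);
- chance of a lower limit within 20 points: below 1% with either.

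**6. When is the lower limit within 20 points of 90%?** Wilson needs 21 positives (lower limit 70.5%) and exact needs 23 (70.3%). With N fixed, 4501/21 = 214 and 4501/23 = 196, so a pathogen at about 1 in 200 or commoner.

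**7. Overall target.** 4501 × 0.10 = 450 positives; 1.96 × √(0.09/450) = 0.028, inside ±3 points.

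**The case against.** The arithmetic is not wrong: both sample sizes reproduce from the stated inputs, and planning on expected counts is ordinary practice. The interval method is not named, so the normal approximation is inferred, and choosing the analysis interval may properly be left to the SAP.

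±20% is normally read as a half-width. On that reading Wilson misses by 0.3 points at 9 positives and a Jeffreys interval meets the target (19.5). Sizing on Jeffreys half-widths would also give 385 and 9 positives, so the inference to the normal formula is not unique. And if the 0.2% counts PCR true positives as Section 5.1 defines them, 9 of these at 90% sensitivity imply 10 culture positives. Wilson at 9/10 then gives 19.3 points, inside the target, and exact gives 22.1, still outside.

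All of this stands, and it rules out saying that the ±20% is simply not delivered. It does not remove the asymmetry. Only 10 points lie above 90%, so a 20-point margin can inform only on the low side. There the distance is 30 points even with Jeffreys (lower limit 60.0%, from Beta(8.6, 1.4)), and 30 to 35 points at 9/10 (lower limits 59.6% Wilson, 55.5% exact). The point also does not depend on the SAP: the protocol itself states a precision at a confidence level as the reason for its N.

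A reader might go further and infer that the study is too small, or that N must rise to 10,500–11,500 (21 or 23 positives divided by 0.002). The documents do not support that. The primary outcome is overall accuracy, and Sections 4.3, 5 and 11.2 define no pathogen-level outcome or analysis. Section 11.1 speaks only of being able to assess performance for uncommon pathogens.

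**Conclusion.** The point holds as a misstatement of precision in the paragraph that fixes N. For a 1-in-500 pathogen about 9 positives are expected. The half-width is about 20 points (Wilson) to 23 points (exact), so the symmetric target is borderline or missed. The lower limit is about 32 to 37 points below the estimate, where a reader would expect 20. This rests on the protocol's own 90% sensitivity and 0.2% frequency, on reading 0.2% as the rate of reference positives, and on every sample giving both a PCR and a culture result. Section 11.3 excludes those that do not, so 9 is if anything optimistic.

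Overall sensitivity keeps its ±3 target with a small margin. The attribution of 4501 to overall sensitivity in Section 7.4, and in the rare-pathogen sentence of 11.1, conflicts with the 3851 in 11.1; this is a wording matter and undersizes nothing. Should be fixed; it does not alter the primary analysis.

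**What to change.** Keep N = 4501 and amend the text.

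- **Section 11.1:** say that about 9 positives are expected for a pathogen at 1 in 500 and that this count will vary (95% range 4 to 15). Give the likely 95% limits: roughly 52–57% to 98–100% if 8 of 9 are detected. Add that a lower limit within 20 points of a 90% estimate needs about 21 (Wilson) to 23 (exact) positives, that is, a pathogen at about 1 in 200 or commoner.
- **Interval method:** state that any pathogen-level sensitivity will carry a Wilson or exact interval.
- **Sections 7.4 and 11.1:** tie overall sensitivity to 3851 (4501 gives about ±2.8 points) and the rise to 4501 to uncommon pathogens. Remove the word overall from the rare-pathogen sentence.
- **Optional:** label estimates for sparse pathogens as descriptive. Any fixed cut-off, such as 20 positives, would be the team's choice and does not follow from the protocol.

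The cost is a text amendment and a less favourable stated precision. No samples are added, and data collection and the primary analysis are unchanged.
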